8.3.3 Ankylosing spondylitis quality of life (ASQoL)

The ASQoL consists of 18 items, each with a score of 0 = no or 1 = yes, so that the sum score ranges from 0 to 18, with higher scores indicating worse quality of life. The questions of ASQoL can be found in appendix 16.8 of the clinical study protocol.

If 6 or fewer items are missing, the missing responses will be imputed with the mean of the available responses from that visit to calculate a total score. If more than 6 items are missing, the total score will be left missing.

The ASQoL total score will be tabulated by visit.

8.3.4 ASAS Health Index (ASAS HI) Questionnaire

The ASAS HI has been developed under the auspices of ASAS to assess health in subjects with all forms of SpA. The questionnaire contains 17 items measuring “functioning, disability and health”, these items are given in appendix 16.9 of the clinical study protocol.

Each statement on the ASAS HI is given a score of 1=I agree OR 0=I do not agree. All item scores are summed up to give a total score that ranges from 0 (good functioning) to 17 (poor functioning).

It is to be noted that items 7 and 8 are not applicable for all subjects. For those subjects who ticked the response “not applicable,” the sum score is analyzed based on $n=16$ or $n=15$, respectively.

Missing data:

A total score can be analyzed if no more than 20% of the data are missing. The total score is calculated as follows for respondents with 1 to a maximum of 3 missing responses:

Sumscore = $[x / (17-m)] \cdot 17$, where x =Item summation score and m =Number of missing items.

Cases with more than 3 missing responses cannot be allocated a total score. The ASAS HI questionnaire assessments will be listed, and the total score will be tabulated by visit.

8.3.5 Short-Form 36-Item Health Survey (SF-36)

The SF-36 (Version 2, standard recall) is a 36-item generic HRQoL instrument that uses a recall period of 4 weeks. Items are grouped into 8 domains as follows: Physical Functioning (10 items), Role Physical (4 items), Bodily Pain (2 items), General Health (5 items), Vitality (4 items), Social Functioning (2 items), Role Emotional (3 items), Mental Health (5 items), and 1 item for perceived stability or change in health (Health Transition) during the last year. The concepts represented by these domains contribute to physical, mental, and social aspects of HRQoL. The items of SF-36 can be found in appendix 16.10 of the clinical study protocol.

For the calculation of the SF-36 domain scores and the component summaries PCS and MCS, the scoring software QualityMetric Health Outcomes™ Scoring Software 4.5 will be used. The norm-based scores (based on the US general population for 2009) will be utilized for analysis.

9 PHARMACOKINETICS AND PHARMACODYNAMICS

9.1 Pharmacokinetics

Not applicable.

9.2 Pharmacodynamics

Not applicable.

10 SAFETY ANALYSES

All safety analyses will be based on the SS.

10.1 Extent of exposure

The number of doses received will be summarized with continuous statistics for the SS.

Duration of exposure to study medication will be calculated as:

$$Dur_{Exp} = date_{Last} - date_{First} + d_{int}$$

where d_{int} represents the dosing interval of 14 days.

The cumulative duration of exposure will be summarized for subjects exposed for at least one day, ≥ 183 days, ≥ 365 days, ≥ 548 days, ≥ 730 days.

Additionally, the subject time at risk will be summarized. Subject time at risk (in days) is calculated as:

$$T_{Risk} = date_{Last} - date_{First} + (5 * t_{1/2})$$

where $t_{1/2}$ is 14 days.

If there is a change of treatment or the last clinical contact occurs prior to completion of the follow-up period, the date of last clinical contact per subject is defined as the maximum of [last visit date including safety follow-up visits, last imputed AE start date, last date of termination or completion, last date of study drug administration, death date] or the clinical cutoff date for ongoing studies if earlier than this maximum date).

In cases where the date of last clinical contact (LastCC) occurs prior to completion of this follow-up period, subject time at risk (in days) will be calculated as:

$$T_{Risk} = date_{LastCC} - date_{First} + 1$$

Subject years at risk is the sum of all relevant subject time at risk (in days) divided by 365.25.

The study medication duration will be listed together with the dates of first and last study medication administration.

10.2 Adverse events

Adverse events with start date prior to first administration of study medication are defined as pre-treatment AEs. No summaries of these events will be produced although they will be included in listings.

Adverse events that started more than 70 days after the last administration of study medication are defined as post-treatment AEs. Such events will not be included in tabulated summaries, but will be listed.

Treatment emergent AEs are all AEs starting on or after the date of first study medication and up to 70 days after the last (most recent) dose of study medication. AEs occurring more than 70 days after the last (most recent) dose will not be considered treatment emergent, regardless of whether this occurs during the safety follow-up period, or after a treatment gap of more than 70 days.

If a start date is missing, then the AE will be considered a treatment emergent adverse event (TEAE). Duration should not be calculated if there is missing stop date information.

If the intensity of an adverse event is unknown, it is considered as severe. If the relationship to study drug is missing, it is considered as related.

Tables showing TEAEs, serious TEAEs, non-serious TEAEs, TEAEs leading to discontinuation of study drug, TEAEs by maximum intensity, TEAEs by relationship, serious TEAEs by relationship, fatal TEAEs by relationship, TEAEs including subject numbers will be provided on the SS.

Additionally, more detailed summaries of TEAEs will be presented, which include the exposure adjusted incidence rate (EAIR) with associated 95% confidence interval, and the exposure adjusted event rate (EAER).

The EAIR is defined as the number of subjects (n) with a specific AE adjusted for the exposure and will be scaled to 100 patient-years:

$$EAIR = 100 \cdot n / \sum_{i=1}^N T_{Exp,i}$$

If a subject has multiple events, the time of exposure is calculated to the first occurrence of the AE of interest. If a subject has no events, the total time at risk is used.

Exact Poisson 95% confidence intervals for incidence rates are calculated using the relationship between the Poisson and the Chi-square distribution (Ulm, 1990):

$$LCL = \chi_{2n, \alpha/2}^2 / 2$$

$$UCL = \chi_{2(n+1), 1-\alpha/2}^2 / 2$$

where n is the number of subjects with a specific AE for the incidence rate of interest and is the basis for the number of the degrees of freedom for the chi-square quantile for the upper tail probability χ^2 .

The EAER will be the number of AEs including repeat occurrences in individual subjects divided by the total time at risk scaled to 100 patient-years and calculated using:

$$EAER = 100 \cdot N_{AE} / \sum_{i=1}^N T_{Risk,i}$$

where N_{AE} is the total number of AEs.

No confidence interval will be computed for EAER.

Where an AE start date is (partially) missing, the AE will be considered TE if possible. Imputation rules provided in Section 4.2 are based on the assumption that if the start date is incomplete, either day only is missing, or day and months are missing, or date is completely missing. Although the algorithms for treatment-emergence depend on the onset date, imputation rules are provided for resolution date as well, as these may be needed for certain statistical analyses, such as an analyses of AE prevalence or AE duration.

Listings based on SS for all AEs will be provided. A glossary for the reported terms will also be generated utilizing SOC, HLT, and PT.

Anticipated SAEs, as described in Section 10.5 of the clinical study protocol, will not be summarized either by any additional tables or listings, as they are included in the standard AE summaries.

AEs of interest will be summarized. The following AEs of interest will be summarized in stand-alone tables:

- Opportunistic infections
- Malignant or unspecified tumors
- Malignant tumors
- Serious cardiovascular events
- Demyelinating-like disorders
- Aplastic anemia, pancytopenia, thrombocytopenia, neutropenia, and leucopenia
- Serious bleeding events

For the following AEs of interest, no additional tables will be provided, as these are included in the standard AE summaries:

- Serious infections
- Congestive heart failure
- Lupus and lupus-like illness
- Serious skin reactions (eg, Stevens Johnson Syndrome, toxic epidermal necrosis, and erythema multiforme)

The following notes to AEs of interest in the clinical study protocol are given for reporting purposes only, and therefore will not be summarized separately: A confirmed LTBI must be reported as an AE of interest. Confirmed active TB is an AE of interest. In the event that an active TB occurrence meets the protocol's SAE criteria, it is also an SAE. Potential Hy's Law, defined as $\geq 3 \times \text{ULN}$ alanine aminotransferase or aspartate aminotransferase with coexisting $\geq 2 \times \text{ULN}$ total bilirubin in the absence of $\geq 2 \times \text{ULN}$ alkaline phosphatase, with no alternative explanation for the biochemical abnormality is also considered an AE of interest.

The following events are not officially considered to be AEs of interest but are nonetheless considered to be interesting enough to be summarized in stand-alone tables: 1) Hepatic events and 2) Hypersensitivity reactions and anaphylactic reactions.

The approach for summarizing AEs of interest is detailed in the

UCB AE of interest program specifications for Cimzia from 18 June 2018.

Data collected on hospitalization will be presented in a listing.

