- Subjects who initiate treatment for LTBI during the Screening Period must repeat initial screening laboratory parameters, examination, and questionnaires (after receiving at least 4 weeks duration of treatment for LTBI) prior to randomization in the study, and must plan to continue the full course of LTBI prophylaxis therapy. The Investigator must assess that the subject's likelihood of completing the therapy is high and duly record his/her opinion in the subject's record prior to randomizing the subject. It is suggested to obtain the opinion of a TB specialist, especially for subjects having been in contact with multi-resistant TB.
- An extension of the Screening Period up to 12 weeks is allowed in order to allow for 8 weeks of LTBI treatment prior to study drug initiation. If the initial 8 weeks of prophylactic LTBI therapy cannot be accomplished with the extended Screening Period, the subject should be considered screen failed.

• Rescreening may occur only after discussion with and approval by the study physician (or Medical Monitor)

Procedure to be followed for subjects with conversion of IGRA or diagnosis of a new TB infection during the Study:

- Conversion is defined as a positive IGRA or 2 indeterminate results at the same visit (scheduled or unscheduled) of the same IGRA method.
- The subject should immediately discontinue study drug intake upon positive test conversion. Should evaluation of the subject by the appropriate TB specialist result in a diagnosis of LTBI, the study drug must be withheld until the appropriate prophylactic therapy has been received for at least 4 weeks and the subject is deemed likely to continue therapy to completion. The treatment must be discussed with the study physician before study drug is restarted.
- If the subject's evaluation reveals active TB infection during the course of the study, the subject must be immediately discontinued from study medication and a WD Visit must be scheduled as soon as possible, but no later than the next scheduled visit. The subject should be encouraged to keep the FU Visit as specified by the protocol.
- Refer to Section 10.4, for instructions on reporting a confirmed LTBI or confirmed active TB occurrence (note that in the event that an active TB occurrence meets the protocol-defined SAE criteria, it is also an SAE).

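### In a dosing gap longer than 70 days followed by a restart, SAP 10.2 stops counting adverse events but SAP 10.1 keeps counting time at risk, so the exposure-adjusted rates can only be equal to or lower than rates on matched definitions

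*SAP*

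**What the plan says.** **Numerator (SAP 10.2).** A treatment-emergent adverse event (TEAE) starts on or after the first dose and "up to 70 days after the last (most recent) dose of study medication". Later events are ruled out: "AEs occurring more than 70 days after the last (most recent) dose will not be considered treatment emergent". The rest of that sentence makes clear that a mid-study interruption is covered as well as follow-up, with the words "or after a treatment gap of more than 70 days". A separate sentence defines post-treatment events as those starting more than 70 days after the last administration. These are listed but not tabulated.

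**Denominator (SAP 10.1).** Subject time at risk is the last dose date minus the first dose date plus five half-lives, with the half-life set at 14 days. A shorter formula (last contact minus first dose plus 1) applies "In cases where the date of last clinical contact (LastCC) occurs prior to completion of this follow-up period". The surrounding text also mentions a change of treatment. It does not mention interruption and restart.

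**Rates (SAP 10.2).** EAER divides all events, repeats included, by summed time at risk. EAIR divides the number of subjects with the event by summed time, which runs to first occurrence for subjects with the event and is total time at risk for the others.

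**Where a restart is foreseen (Protocol 10.6.4.1).** After conversion of the tuberculosis test and a diagnosis of latent infection, "the study drug must be withheld until the appropriate prophylactic therapy has been received for at least 4 weeks". Dosing may then restart after discussion with the study physician. The readable text gives no maximum length for the hold.

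**The concern.** An exposure-adjusted rate should count time only while an event could enter the numerator. At the end of treatment the SAP respects this, because the TEAE window and the tail of time at risk are both 70 days. Inside a long gap it does not. The numerator rule was written with gaps in mind, and the denominator was not changed to match.

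The direction of the error is fixed: uncountable days enlarge the denominator and can add nothing to the numerator. TEAEs are the secondary safety variable, and EAIR and EAER are how the SAP delivers the per-100-patient-year correction promised in Protocol 12.4.1. What is at stake is a slight understatement of those rates, and a definition that two programmers could implement differently.

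**Working it through.** The documents state no EAIR or EAER value, so there is no figure to reproduce. The check compares the two definitions and then sizes the difference.

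**Inputs from the documents**
- TEAE window after the most recent dose: 70 days (SAP 10.2)
- Tail of time at risk: 5 × 14 = 70 days (SAP 10.1)
- Planned last dose: Week 94, so day 94 × 7 = 658 (SAP 3.6)
- Planned number of subjects: 86 (SAP 2)

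**Assumption.** The number and length of gaps are not given, so a range is shown. Every subject is taken as a completer with the last dose at Week 94.

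**Step 1: the rules agree without gaps.** A completer has 658 + 70 = 728 days at risk, which ends at Week 104. The TEAE window closes on the same day.

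**Step 2: threshold.** For a gap of G days between consecutive doses, the uncountable days left in the denominator are max(0, G − 70). Four missed two-weekly doses give G = 5 × 14 = 70, so 0 days. Five give G = 6 × 14 = 84, so 14 days.

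**Step 3: effect on EAER.** Let N be the event count, ΣT the SAP denominator and E the total of uncountable days. The SAP rate is proportional to N/ΣT and the matched rate to N/(ΣT − E). Their ratio is 1 − E/ΣT, which does not depend on the event rate. Here ΣT = 86 × 728 = 62,608 days, or 171.4 patient-years.

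EAER understatement (100 × E/ΣT), by number of subjects with one such gap:

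| Gap (days) | Uncountable days each | 1 | 3 | 5 | 10 |
|---|---|---|---|---|---|
| 42 or 70 | 0 | 0% | 0% | 0% | 0% |
| 84 | 14 | 0.02% | 0.07% | 0.11% | 0.22% |
| 112 | 42 | 0.07% | 0.20% | 0.34% | 0.67% |
| 182 | 112 | 0.18% | 0.54% | 0.89% | 1.79% |
| 364 | 294 | 0.47% | 1.41% | 2.35% | 4.70% |

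For example, five 182-day gaps give 5 × 112 / 62,608 = 0.89%. With an assumed matched rate of 200 events per 100 patient-years, the SAP would report 198.2. The 364-day row is an extreme: a hold beginning at Week 48 leaves only (94 − 48) × 7 = 322 days to the planned last dose.

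**Step 4: effect on EAIR.** The excess days enter only for subjects with no occurrence of that event before them; a subject with an earlier event is already cut off at that event. The symbol for exposure time in the EAIR formula is not defined. Duration of exposure (last minus first dose plus 14 days) and time at risk both run through gaps, so the direction is the same for either.

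**Step 5: the latent tuberculosis route.** Four weeks of prophylaxis take 28 of the 70 days. The remaining 42 have to cover the time since the last dose, the specialist's evaluation and any wait before restart. A hold near the minimum therefore has no effect. A slow work-up or a longer course before restart could pass the threshold.

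**The case against.** The strongest case against is that the point is too small and too rare to matter. Nothing happens until five consecutive doses are missed and dosing then resumes. The documents do not show that such gaps are expected. The latent tuberculosis hold has a four-week minimum, and of the two scheduled on-treatment tests only Week 48 precedes the last dose (unscheduled tests are allowed). Protocol 7.7 mentions doses missed because of an adverse event, but that is a compliance rule and says nothing about gap length or restart. EAIR and EAER come in SAP 10.2 as additional, more detailed summaries; TEAE counts and percentages do not use this denominator. The study has one arm, so no between-arm safety comparison is biased, and the primary analysis has its own time offset (SAP 8.1.1).

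All of this stands, and it limits the size. It does not remove the mismatch, because the SAP itself provides for gaps over 70 days and does so on one side of the ratio only.

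A reader might infer three stronger things that the documents do not support:
- **That any interruption and restart lowers the rates.** Gaps up to 70 days leave them unchanged.
- **That a single interrupted subject's figure, such as 112/728 = 15.4% for a 182-day gap, is an error in a reported result.** Both rates are pooled and no subject-level rate is planned.
- **That events in a gap fall outside every class and are lost.** SAP 10.2 says they are not treatment-emergent, and all events are listed. What remains is a loose label: the post-treatment sentence refers to the last administration without the most-recent-dose gloss used for TEAEs.

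**Conclusion.** The mismatch is real and is in the current SAP text. It acts only when consecutive doses are more than 70 days apart and dosing then restarts. In that case EAER, and EAIR for subjects without an earlier event, can only be equal to or lower than the rates on matched definitions.

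The size rests on assumed gaps: below 1% for up to five of 86 subjects with 182-day gaps, and about 1.8% for ten. A 1% shift in EAER needs about 626 uncountable days (0.01 × 62,608), which is six subjects with such gaps. Early withdrawals would reduce ΣT and raise these percentages somewhat. No TEAE count, no percentage of subjects and no efficacy result is affected. This is a minor definitional error, worth correcting because it is one-directional and cheap to fix.

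**What to change.** - **SAP 10.1:** define time at risk as the union of the intervals from each dose to 70 days after it, cut at last clinical contact. Without long gaps this gives the current value.
- **SAP 10.2:** use that time for both rates. For EAIR, accumulate it to the first countable occurrence, or in full if there is none, and define the exposure symbol accordingly.
- **SAP 10.2:** word the post-treatment class in terms of the most recent dose, so that events in a gap beyond day 70 are labelled off-treatment and listed only, as they are now.

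The cost is one extra derivation and slightly fewer patient-years. Administration dates are already used dose by dose for compliance (SAP 7 and Appendix 12.1), so no new data are needed. A short rule is needed for a dose given on an unknown date, because the compliance convention of a 14-day deviation does not settle whether the subject was at risk.

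### The confidence limits printed for the exposure-adjusted incidence rate are limits for a count of subjects, so they are on the wrong scale and can exclude the estimate

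*SAP*

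**What the plan says.** SAP section 10.2 describes the EAIR as the "number of subjects (n) with a specific AE adjusted for the exposure and will be scaled to 100 patient-years", and its formula is 100 times n over the sum of the individual exposure times T_Exp. On exposure it says: "If a subject has multiple events, the time of exposure is calculated to the first occurrence of the AE of interest". Subjects without the event contribute their total time at risk.

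The interval is introduced with "Exact Poisson 95% confidence intervals for incidence rates are calculated using the relationship between the Poisson and the Chi-square distribution", and two formulas follow:

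- lower limit: "LCL = \chi_{2n, \alpha/2}^2 / 2"
- upper limit: "UCL = \chi_{2(n+1), 1-\alpha/2}^2 / 2"

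The text then explains n: "where n is the number of subjects with a specific AE for the incidence rate of interest". Neither section 10.1 nor section 10.2 says that the limits are afterwards divided by exposure or multiplied by 100. The Amendment 3 log (SAP section 13.3) gives the same two formulas as the new wording, so this is the current text. Protocol section 12.4 says only that adverse event data will be corrected for exposure per 100 patient-years.

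**The concern.** The estimate and its interval are on different scales. The EAIR is a rate per 100 PY; the limits depend on n alone and would be the same whether n subjects were affected over 50 PY or 170 PY. An interval that does not respond to exposure cannot be an interval for an exposure-adjusted rate.

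If the formula is programmed as printed, every EAIR interval in the detailed tables of treatment-emergent adverse events is misplaced and has the wrong width, unless exposure for that row is exactly 100 PY. For uncommon events the result looks plausible, so nobody would notice. For very common events the interval may fail to contain its own estimate. Treatment-emergent adverse events are the secondary safety variable (SAP section 2.2.2.1), and these tables are where a reader would look for the precision of each rate.

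**Working it through.** The documents give no numerical EAIR or interval, so there is no stated figure to reproduce. The check evaluates the printed formulas and compares them with the scaled ones.

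**Inputs.** Two-sided 95%, so 0.025 per tail (SAP 10.2). N = 86 subjects and average follow-up of 1.5 years (SAP 2.4), giving 86 × 1.5 = 129 PY. Maximum time at risk under SAP 10.1, with last dose at Week 94: 94 × 7 + 70 = 728 days = 1.99 years, or at most 171.4 PY for 86 subjects. Actual exposure is not in the documents, so every n and PY below is illustrative.

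**Step 1: what the printed limits are.** Write L(n) = χ²(2n; 0.025)/2 and U(n) = χ²(2(n+1); 0.975)/2, using lower-tail quantiles. For n = 1, 5, 10, 20 and 43, the Poisson probability of n or more events at mean L(n) is 0.025, and of n or fewer at mean U(n) is 0.025. They are therefore the exact limits for a Poisson mean count. Examples: n = 5 gives 1.62 to 11.67; n = 10 gives 4.80 to 18.39.

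**Step 2: what the rate needs.** Since EAIR = 100n/PY, its limits are 100·L(n)/PY and 100·U(n)/PY. Printed limit divided by correct limit is PY/100 at both ends.

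**Step 3: numbers.** For n = 10 and 129 PY: EAIR = 1000/129 = 7.75; correct limits are 100 × 4.795/129 = 3.72 and 100 × 18.390/129 = 14.26. The same arithmetic gives:

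| n | PY | EAIR | As printed | Correct |
|---|---|---|---|---|
| 5 | 129 | 3.88 | 1.62 to 11.67 | 1.26 to 9.05 |
| 10 | 129 | 7.75 | 4.80 to 18.39 | 3.72 to 14.26 |
| 60 | 70 | 85.7 | 45.8 to 77.2 (excludes the EAIR) | 65.4 to 110.3 |

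**Step 4: are such exposures reachable?** Exposure stops at first occurrence, so common events shrink the denominator. Assume a constant hazard h in 86 subjects followed for τ years: h = −ln(1 − n/86)/τ and PY = n/h.

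| τ (years) | n | PY | EAIR | As printed | Correct |
|---|---|---|---|---|---|
| 1.5 | 10 | 121.3 | 8.24 | 4.80 to 18.39 | 3.95 to 15.16 |
| 1.5 | 60 | 75.2 | 79.8 | 45.8 to 77.2 (excludes) | 60.9 to 102.7 |
| 1.5 | 77 | 51.2 | 150.5 | 60.8 to 96.2 (excludes) | 118.8 to 188.1 |
| 1.99 | 60 | 100.0 | 60.0 | 45.8 to 77.2 | 45.8 to 77.3 |
| 1.99 | 77 | 68.0 | 113.2 | 60.8 to 96.2 (excludes) | 89.4 to 141.5 |

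Under this assumption the printed interval excludes the EAIR for every n from 59 to 85 at 1.5 years, and from 72 to 85 at 1.99 years. Below those counts it contains the estimate but is on the wrong scale. The correctly scaled interval contained the estimate in every case computed.

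**The case against.** The strongest reply is that the intended scale is clear. The section announces intervals for incidence rates, the estimate is stated per 100 PY, and the method is cited to a published source that may supply the division. On this view the display omits an obvious last step that any programmer would add. It is also true that the documents contain no output, so nobody can say that wrong intervals have been produced. The wording that Amendment 3 replaced asked for an exact chi-square interval without spelling out the scaling either, so the amendment did not remove a correct instruction.

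That limits the charge but does not answer it. Scaling was probably meant, yet the current text gives an explicit formula that is wrong if followed. Two programmers working from it could agree with each other and both be wrong.

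The objection that exclusion of the estimate is confined to very common rows, such as any treatment-emergent event, also stands under the constant-hazard model: at 1.99 years and n = 60 the exposure happens to be 100.0 PY and the error all but vanishes. The 129 PY example uses full follow-up for affected subjects as well; stopping their exposure at first event gives 121.3 PY and an EAIR of 8.24 instead of 7.75, a small change that leaves the point intact.

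Finally, the consequence is bounded. The trial has one arm, the event counts, percentages, EAIR estimates and event rates are unaffected, and Protocol section 12.2 treats everything beyond the primary efficacy analysis as exploratory.

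**Conclusion.** The formula is wrong as written. It gives exact limits for the number of subjects affected and labels them as limits for a rate. Each limit is off by the factor PY/100: at 129 PY both are 29% too high, and at 70 PY both are 30% too low. The scale error itself needs no assumption beyond total exposure differing from 100 PY. How often the interval excludes its estimate does depend on assumptions: with a constant hazard and 86 subjects it happens only for events affecting at least 59 subjects at 1.5 years, or at least 72 at 1.99 years. The primary analysis and the sample size are untouched. The correction should be made because the affected intervals describe the secondary safety variable.

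**What to change.** In SAP section 10.2, replace the two limits with:

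- LCL = 100 × χ²(2n; α/2) / (2 × ΣT_Exp,i)
- UCL = 100 × χ²(2(n+1); 1 − α/2) / (2 × ΣT_Exp,i)

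Define T_Exp,i beside the formula, in patient-years: time from first dose to first occurrence of the event for subjects who have it, and total time at risk otherwise, in days divided by 365.25. Section 10.2 already gives the rule for which time to use, but section 10.1 defines only exposure duration and time at risk, both in days, and does not define T_Exp.

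Also state that the quantiles are lower-tail. The present note refers to an upper tail probability, which does not fit the subscripts: read that way, the lower limit would exceed the upper.

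The cost is one formula and its definition. No data collection, sample size or other analysis changes. If the tables have already been programmed, check one row by hand against the scaled formula.
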